### 12.5 Subgroup Analyses

Due to the small sample size, no subgroup analyses will be performed.

## 13 Safety analyses

### **13.1** Treatment exposure

Exposure to study drug (prescribed daily dose, actual daily dose received and duration of treatment) will be summarized by dose group (2 and 4 mg/kg/day) with descriptive statistics.

#### 13.2 Adverse events

All AEs will be coded using MedDRA version 21.1.

A TEAE is defined as an AE with a start date/time after the first administration of IMP and within 28 days after stopping therapy.

The number and percentage of patients with at least one TEAE, at least one severe TEAE, at least one serious TEAE, including death, at least one non-serious TEAE, any related TEAE, any fatal TEAE, any TEAE leading to study drug withdrawn and any TEAE leading to study withdrawal will be summarized.

The number and percentage of patients with at least one TEAE will be summarized in frequency tables by treatment, system organ class and preferred term. Separate tables will present TEAEs classified by relationship to investigational product and TEAEs classified by maximum severity. These tables will be presented by PT in descending order of frequency in the anakinra group. Percentages will be based on the number of patients in the safety analysis set for the specific treatment group.

The number of patients with MAS will be reported.

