6.5.5.1.2 Adverse event reporting period

SAEs should be recorded within the CRF, from the time the patient has signed the informed consent until 4 weeks past the last dose of IMP. See Figure 2. Non-serious AEs will be recorded within the CRF from the first administration of IMP until 4 weeks past the last dose of IMP. Furthermore any SAE, if a causal relationship between the event and the IMP(s) is suspected, which occurs after last study visit/telephone follow-up, should be reported (see 6.5.5.1.4).

Refer to section 6.5.5.1.6 for information how unresolved adverse events and SAEs should be followed up.

Figure 2 Adverse event report period

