# 8.2.2 Imputation of Adverse Event start dates

To assess if AEs are treatment emergent, missing onset dates will be imputed according to the following rules:

- If day is missing and month and year of AE onset is the same as the month and year of first dose of study treatment, then the onset date of the AE will be assumed to be the same as the date of first dose of study treatment.
- If day and month is missing and year of AE onset is the same as year of first dose, then the date of onset will be assumed to be the same as the first dose of study treatment.
- Otherwise, if day is missing, then use YYYY-MM-01, and if day and month are missing, then use YYYY-JAN-01.
- Completely missing onset dates will not be imputed. AEs with a completely missing onset date will be considered treatment-emergent.

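### The SAP imputes some partial AE onsets to the first-dose date but requires a TEAE to start after first administration, and gives no rule for the tie

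*SAP*

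**What the plan says.** Three places in the documents bear on this.

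- **Boundary (SAP 13.2).** "A TEAE is defined as an AE with a start date/time after the first administration of IMP and within 28 days after stopping therapy". The overview, SOC/PT, relationship and severity tables in 13.2, the serious-event table in 13.2.1 and the withdrawal table in 13.2.2 are all built on TEAEs.
- **Imputation (SAP 8.2.2).** Its purpose is explicit: "To assess if AEs are treatment emergent, missing onset dates will be imputed according to the following rules". The first rule covers an onset whose day is unknown but whose month and year match those of the first dose; its outcome is "then the onset date of the AE will be assumed to be the same as the date of first dose of study treatment". The second applies the same value under the condition "If day and month is missing and year of AE onset is the same as year of first dose". Other partial dates follow a different rule: "Otherwise, if day is missing, then use YYYY-MM-01, and if day and month are missing, then use YYYY-JAN-01". Finally, "AEs with a completely missing onset date will be considered treatment-emergent". None of these rules assigns a clock time.
- **Collection window (Protocol 6.5.5.1.2).** "Non-serious AEs will be recorded within the CRF from the first administration of IMP until 4 weeks past the last dose of IMP". SAEs are collected from informed consent.

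Protocol 6.4.3.1 and SAP 8.5.6 have the exact time of the Day 1 dose recorded. Neither document says whether AE onset time is collected.

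**The concern.** The imputation and the definition are meant to work as a pair: the first supplies a date so that the second can classify the event. Where the imputed date is the first-dose date, the pair does not fit. A strict inequality applied to two equal dates excludes the event that the imputation was written to classify. The ordering is also odd. An AE with no onset information counts as treatment-emergent, while one known to fall in the dosing month may not.

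What is at stake is the completeness of the AE tables for the earliest part of treatment. Protocol 8.3.7.1 planned AE frequency tables without a treatment-emergence filter; the SAP adds the filter. It specifies a listing for SAEs but none for non-serious AEs, so a non-serious event that fails the filter has no other specified AE table or listing in which to appear. The only other specified use of AEs that is not limited to TEAEs is the review of ADA in relation to AEs (SAP 15).

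**Working it through.** The plan states no figure to reproduce. The check applies the SAP 8.2.2 rules and then the SAP 13.2 start boundary to typical cases.

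**Assumption for illustration:** first dose on 12 March 2019 at 10:00. The date is arbitrary.

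**Three readings of the boundary:**

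- A: onset date later than first-dose date.
- B: onset date/time later than first-dose date/time, with a missing time read as 00:00.
- C: onset date on or after first-dose date.

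| Recorded onset | Date used | A | B | C |
|---|---|---|---|---|
| March 2019, day missing | 12 Mar 2019 (imputed) | no | no | yes |
| 2019 only | 12 Mar 2019 (imputed) | no | no | yes |
| 12 March 2019, no time | 12 Mar 2019 | no | no | yes |
| April 2019, day missing | 1 Apr 2019 (imputed) | yes | yes | yes |
| 2020 only | 1 Jan 2020 (imputed) | yes | yes | yes |
| February 2019, day missing | 1 Feb 2019 (imputed) | no | no | no |
| 13 March 2019 | 13 Mar 2019 | yes | yes | yes |
| Nothing recorded | none | by rule | by rule | by rule |

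Only the start boundary was tested, not the 28-day end.

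**Result.** Three of the eight cases depend on the reading, and all three have a date equal to the first-dose date. They fail on A and B and pass on C. The other five do not change. Partial dates in a later month or year are safe, and a partial date in an earlier month stays excluded on every reading.

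**Is exclusion wrong?** For a non-serious AE, yes. Protocol 6.5.5.1.2 starts CRF recording at first administration, so an event properly in the database began at or after it. For an SAE the answer is open, because collection starts at consent and a Day 1 onset may really precede the dose.

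**Which outputs are exposed?** The TEAE tables in SAP 13.2 to 13.2.2. Not limited to TEAEs are the SAE listing (13.2.1), the deaths listed with it (13.2.3), the count of patients with MAS (13.2) and the ADA-AE review (15).

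**Scale of one patient.** SAP 4.2 and 6 expect at least 12 patients at 2:1. If the split is exact, 12 × 2/3 = 8 on anakinra and 12 × 1/3 = 4 on placebo. If a misclassified event is a patient's only event of its type, the percentage for that type moves by 1/8 = 12.5 points on anakinra or 1/4 = 25 points on placebo. At the originally planned 54 and 27 the shifts would be 1/54 = 1.9 and 1/27 = 3.7 points.

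**The case against.** The strongest reply is that exclusion is not a foregone conclusion. SAP 13.2 speaks of date and time together, and a date without a time is indeterminate against such a test, not false. SAP 8.2.2 exists to classify AEs and counts even undated ones, so the two sections read together point to inclusion. This stands as far as it goes: the outcome depends on how the comparison is programmed. It does not remove the conflict, because the written boundary points one way, the evident intent points the other, and nothing in the SAP decides between them.

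Other limits also stand:

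- The Day 1 case depends on onset time not being collected. If the CRF collects it, a reaction to the supervised first injection is timed and counted.
- Affected events may be few or none. AEs are asked about at Day 4, Week 1, Week 2 and Week 4, so a missing onset day in the first-dose month should be uncommon.
- The safety output is descriptive, and no hypothesis test is touched.

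A reader might infer that these events will certainly vanish from all AE reporting. The documents do not support that: only onsets equal to the first-dose date are exposed, only in TEAE tables, and only on the literal reading. A reader might also infer that injection-site reactions would be hit hardest. Protocol 4.3 says they are typically reported in the first 4 weeks; it does not place them on Day 1, and those with a known later date are unaffected.

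**Conclusion.** The concern holds as a conflict between two stated SAP rules. Followed literally, SAP 13.2 excludes onsets that SAP 8.2.2 sets to the first-dose date, and also Day 1 onsets without a time if none is collected. For non-serious AEs the resulting error can go only towards fewer reported events.

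The size cannot be derived from the documents, since nothing indicates how many onsets will be partial or untimed. The shifts of 12.5 and 25 points are single-patient illustrations. They assume the minimum of 12 patients, an exact 8:4 split and an event that is the patient's only one of its type; they shrink if more patients are randomized. They should not be read as an expected effect.

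This should be settled before database lock. It is a modest correction, but the SAP is to be final before unblinding (SAP 5.2), and a safety classification should not be left to an unwritten programming choice.

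**What to change.** In SAP 13.2, change the start boundary so that a TEAE is an AE that starts on or after the first administration of IMP, judged by date and time where both are known. Add one sentence: an AE whose onset date equals the first-dose date and has no time, or was imputed to that date under 8.2.2, is treatment-emergent unless the record shows that it began before dosing. The exception matters mainly for SAEs, which are collected from consent. SAP 8.2.2 and the 28-day end of the window can stay as they are.

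The cost is two sentences and the matching line of programming before database lock. No new data are needed and no efficacy analysis changes. In the cases tested, the three ties become TEAEs and the other five keep their classification.

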#### 13.2.1 Serious adverse events

The number and percentage of patients with at least one serious TEAE will be tabulated by SOC and PT. SAEs will also be listed. The listing will include information on treatment group, age, sex, race, start/stop date of event, SOC/PT, causality, severity, action taken, and outcome.

#### 13.2.2 Adverse events leading to withdrawal

The number and percentage of patients with TEAEs leading to study withdrawal will be presented by SOC and PT.

#### **13.2.3** Deaths

Details of any deaths will be listed together with SAEs as detailed in 13.2.1.

### 13.3 Laboratory data

The laboratory data evaluation will be based on the results from the central laboratory.

The laboratory safety data will be presented as actual values and change from baseline values over time by descriptive statistics. The number and percentage of patients with low, normal, or high laboratory values at baseline versus subsequent visits will be presented using shift tables.

The values at post-baseline visits versus baseline for each laboratory parameter will be presented in shift plots.

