Anakinra is a recombinant IL-1 receptor antagonist (IL-1Ra) that blocks the biological activity of cytokine IL-1 (IL-1 α and IL-1 β) by competitively inhibiting its binding to the IL-1 type I receptor and thereby controlling active inflammation. Anakinra has a short half-life and is self-administered as a daily s.c. injection.

Kineret[®] is currently approved in the US (2001), Canada (2002), and EU/EEA (2002) for the treatment of RA. Kineret is also approved for the most severe form of CAPS, i.e., NOMID, in the US (2012), and for all forms of CAPS in EU/EEA (2013). In addition, Kineret is approved for the treatment of SJIA in Australia (2015) and for Still's disease, including SJIA and AOSD in EU (2018).

In the currently available data there are no relevant differences in the safety profile between pediatric and adult patients. Neither are there any relevant differences in the safety profile of patients with Still's disease compared to patients with other indications for anakinra treatment. However, post marketing reports describing hepatic events and events of MAS are over-represented in patients with Still's disease, especially in pediatric patients.

Hepatic events, mainly liver enzyme elevations, but also cases of non-infectious hepatitis, have been associated with anakinra. Hepatic events during post marketing use have mainly

been reported in patients with predisposing factors, e.g., history of transaminase elevations before start of anakinra treatment. Hepatic events are common manifestations of Still's disease and hepatic events occur also in anakinra-treated patients with Still's disease.

Cases of MAS have been described in anakinra-treated patients with Still's disease, both in publications and in spontaneous reports during post marketing use. However, patients with Still's disease, both pediatric and adults, have an increased risk for spontaneous development of MAS. A causal relationship between anakinra and development of MAS has not been established.

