6.3.2 Exclusion criteria

The presence of any of the following will exclude a patient from inclusion in the study:

1. Diagnosis of Still's disease more than 6 months prior to randomization.
2. Previous randomization into this study
3. Participation in another concurrent clinical interventional study within 30 days of randomization.
4. Treatment with an investigational drug within 5 half-lives prior to randomization.
5. Previous or current treatment with anakinra, canakinumab or any other IL-1 inhibitor.
6. Use of the following therapies prior to randomization:
 - Narcotic analgesics within 24 hours prior to randomization
 - Dapsone or etanercept within 3 weeks prior to randomization
 - Intraarticular, intramuscular or intravenous administration of glucocorticoids or intravenous Ig within 4 weeks prior to randomization
 - Intravenous Ig with proven Still's disease modifying effect, leflunomide, infliximab, or adalimumab within 8 weeks prior to randomization

- Thalidomide, cyclosporine, mycophenolate mofetil, 6-mercaptopurine, azathioprine, cyclophosphamide, chlorambucil, or any other immunosuppressant within 12 weeks prior to randomization
 - Tocilizumab within 12 weeks prior to randomization or any other immunomodulatory medication within 4 half-lives prior to randomization
 - Rituximab within 26 weeks prior to randomization
7. Live vaccines within 1 month prior to randomization.
 8. Known presence or suspicion of active, chronic or recurrent bacterial, fungal or viral infections, including tuberculosis, HIV infection or hepatitis B or C infection.
 9. Clinical evidence of liver disease or liver injury as indicated by presence of abnormal liver tests
 - AST or ALT >5 x ULN, *or*
 - AST or ALT >3 x ULN accompanied by elevated bilirubin >2 x ULN.
 10. Presence of severe renal function impairment CKD stages 4 and 5 (estimated creatinine clearance < 30 mL/min/1.73m²).
 11. Presence of neutropenia (ANC < 1.5 x 10⁹/L).
 12. Presence or suspicion of MAS at baseline. (See Appendix 2 for guidance).
 13. A diagnosis of MAS within 2 months prior to randomization.
 14. History of malignancy within 5 years. Exceptions are basal cell skin cancer, carcinoma-in-situ of the cervix or low-risk prostate cancer after curative therapy.
 15. Known hypersensitivity to E coli-derived proteins, or any components of Kineret (anakinra).
 16. Pregnant or lactating women.
 17. Foreseeable inability to cooperate with given instructions or study procedures.

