#### **8.1** Time windows

For the purpose of the statistical analysis and if not otherwise specified, all the variables (primary, secondary and exploratory variables) will be assigned to the visit/assessment timepoint in which they were collected depending on the following analysis time windows in Table 1.

Table 1 Time windows

Visit	Week	Study Day	Study Day window
1	Baseline	1	≤1
2	1	8	2-11
3	2	15	12-22
4	4	29	23-43
5	8	57	44-71
6	12	85	≥ 72

Unscheduled visit data will be considered when assigning assessments to the analysis visit. If more than one assessment of the variable (scheduled or unscheduled) falls in the same time window but on different days, the closest to the scheduled visit day will be taken, or the earlier, in the event the values are equidistant from the nominal visit date. If several measurements are collected during the selected day, the average (for numeric values)/worst (for categorical values) of the measurements will be taken.

In summaries of extreme values as opposed to visit-based summaries, all post baseline values collected are used including those collected at unscheduled visits regardless if the value is closest to the scheduled visit date or not. For summaries at a patient level, all values should be included, regardless of whether they appear in a corresponding visit-based summary, when deriving a patient level statistic such as a maximum.

Listings will display all values contributing to a time point for a patient.

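### SAP 13.3 reports laboratory data only by visit, with one value kept per window, so an off-schedule peak can be missing from every laboratory table and plot

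*SAP*

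**What the plan says.** SAP 13.3 bases the laboratory evaluation on central-laboratory results and names three outputs: descriptive statistics of actual values and changes over time, shift tables, and shift plots of values at post-baseline visits against baseline. For the shift tables: "The number and percentage of patients with low, normal, or high laboratory values at baseline versus subsequent visits will be presented using shift tables." It names no worst post-baseline summary, no summary by multiples of ULN and no laboratory listing.

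SAP 8.1 decides which value represents a visit. Off-schedule data are eligible: "Unscheduled visit data will be considered when assigning assessments to the analysis visit." When several values on different days share a window, "the closest to the scheduled visit day will be taken, or the earlier, in the event the values are equidistant from the nominal visit date." For summaries of extreme values, in contrast to visit-based ones, "all post baseline values collected are used including those collected at unscheduled visits." On listings: "Listings will display all values contributing to a time point for a patient."

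Protocol 6.3.2 excludes patients on transaminases only for "AST or ALT >5 x ULN", or for AST or ALT above 3 x ULN together with bilirubin above 2 x ULN. Patients can therefore enter with clearly raised values, and Protocol Appendix 1 counts liver dysfunction among the minor criteria for adult-onset disease. Protocol 4.1 says that "post marketing reports describing hepatic events and events of MAS are over-represented" in patients with Still's disease.

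**The concern.** A sample taken at a discontinuation or unscheduled visit is often taken because something has changed. Protocol 6.5.5.6 asks for the full laboratory panel at the Study Drug Discontinuation visit even in children under 15 kg, whose blood volume is otherwise spared. If that result falls in the same window as a scheduled result nearer the nominal day, it drops out of all three outputs in SAP 13.3. SAP 8.1 contains the rule that would keep it, but 13.3 plans no summary to which that rule applies.

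The shift table has a second limit. A patient who starts above ULN and rises further stays in the high-to-high cell, whatever the size of the rise.

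The study is small enough for one value to matter. SAP 4.2 expects at least 12 randomized patients at 2:1, so about 12 x 2/3 = 8 on anakinra and 4 on placebo if the number is 12. A single displaced peak could be the only signal of its kind.

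**Working it through.** The documents give no figure for displaced laboratory values, so there is none to reproduce. The check applies the SAP 8.1 rule to each possible stop day.

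**Inputs**
- Windows (SAP 8.1, Table 1): Week 1, Days 2-11; Week 2, Days 12-22; Week 4, Days 23-43; Week 8, Days 44-71; Week 12, Day 72 onward. Nominal days are 8, 15, 29, 57 and 85.
- Selection (SAP 8.1): nearest to the nominal day; a tie goes to the earlier value.
- A discontinuation at a scheduled visit before Week 12 replaces that visit (Protocol 6.1).
- A patient who stops before Week 2 still has the Week 2 visit, unless the discontinuation visit falls within the 3 days before it (Protocol 6.1).
- Visit tolerance (Protocol Appendix 5): +2 days at Weeks 1 and 2; plus or minus 2 days at Weeks 4, 8 and 12.
- Assumptions: earlier scheduled visits took place and gave a result for the parameter; a patient who stops before Week 1 has no separate Week 1 visit; every stop day counts once.

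**Rule.** The stop-day value is displaced if another value in its window is nearer the nominal day, or equally near and earlier.

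**Visits on nominal days.** Possible stop days are 2 to 84, which is 83 days.

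| Window | Stop days in window | Days on which the stop value is displaced |
|---|---|---|
| Week 1 | 10 | 9-11: 3 |
| Week 2 | 11 | 16-22: 7 |
| Week 4 | 21 | 30-43: 14 |
| Week 8 | 28 | 58-71: 14 |
| Week 12 (to Day 84) | 13 | 0 |
| Total | 83 | 38 |

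38/83 = 46%. After Week 2 (Days 16-84) it is (7 + 14 + 14)/69 = 35/69 = 51%. Over Days 2-29 it is (3 + 7)/28 = 36%, because Days 30-43 and 58-71 supply 28 of the 38 days.

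**Visits two days late** (Days 10, 17, 31, 59, 87). Stop days are 2 to 86, which is 85 days. Displaced: Days 11, 12, 18-22, 32-43 and 60-71, that is 1 + 1 + 5 + 12 + 12 = 31. 31/85 = 36%.

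**Weeks 4, 8 and 12 two days early** (Days 27, 55, 83). Stop days are 2 to 82, which is 81 days. Displaced: Days 9-11, 16-22, 31-43 and 59-71, that is 3 + 7 + 13 + 13 = 36. 36/81 = 44%.

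**Unscheduled values on non-visit days, every scheduled visit done.** Displaced on 79 of 79 days with nominal timing, 71 of 77 (92%) with Weeks 4, 8 and 12 two days early, and 61 of 81 (75%) with visits two days late.

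**Shift categories.** Take an illustrative AST of 2 x ULN at baseline and 10 x ULN later (assumed values). Both are high, so the shift table shows no change. If the later value is the selected one, it enters the change from baseline, the visit maximum (SAP 8 includes minimum and maximum) and the shift plot.

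**Under an all-values rule.** A worst post-baseline summary uses every central value, so displacement is zero by construction.

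**The case against.** The strongest reply is that little would be hidden in practice, and much of it stands.

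- A reader might infer that transaminase rises from a high baseline vanish. They do not if the value is selected: two of the three outputs in 13.3 are numeric, and in about 12 patients an outlying point would stand out.
- A reader might infer that unscheduled values are excluded. SAP 8.1 makes them eligible; they lose only to a value that is nearer, or as near and earlier.
- A reader might extend the grading point to neutropenia. Protocol 6.3.2 excludes ANC below 1.5 x 10^9/L, so a later fall to low is a visible shift if that value is selected.
- Important values have another route. Protocol 6.5.5.1.1 and 6.5.5.6 call for an AE when a result is clinically significant or leads to stopping treatment, and SAP 13.2 tabulates TEAEs.

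The AE route narrows the gap but does not close it. It depends on investigator judgement. Protocol 6.5.5.1.1 does not record worsening of Still's disease as an AE unless it is serious, and Protocol 4.1 calls hepatic events common manifestations of the disease. A non-serious rise attributed to the disease may therefore go unrecorded as an AE. The listing sentence in SAP 8.1 is ambiguous: a displaced value may not count as contributing to a time point, and 13.3 names no laboratory listing.

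**Conclusion.** The concern holds in a limited form. SAP 13.3 combined with SAP 8.1 allows an off-schedule peak to be absent from every laboratory table and plot, and no planned laboratory summary uses the rule that would retain it. A discontinuation value is displaced on 46% of possible stop days with nominal timing, 44% with the later visits two days early and 36% with visits two days late.

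These are shares of calendar days. It is tempting to read them as the share of patients or of discontinuation values lost. The documents do not support that: they give no distribution of stop days, and discontinuations at a scheduled visit always keep their value. The percentages also rest on the visit-timing assumptions in the check.

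The grading limit belongs to the shift table alone and matters for analytes already high at entry. This is a worthwhile gap in safety reporting; it does not show that a safety signal will be lost.

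**What to change.** In SAP 13.3 add, for each laboratory parameter, a shift from baseline to worst post-baseline value. Use all central-laboratory values (scheduled, discontinuation and unscheduled) and cite the extreme-values rule of SAP 8.1. State for each parameter whether worst means highest, lowest or both.

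In that table show AST/ALT and bilirubin by multiples of ULN, for example at the protocol's own entry limits: 3 and 5 x ULN for AST/ALT, and 2 x ULN for bilirubin. These are display bands only. They are not a toxicity grading and carry no consequence for patient management.

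Flag values taken after the last dose. A patient who stops before Week 2 may return for the Week 2 visit off study drug, and that value should be identifiable.

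The cost is one extra table and a few lines of SAP text, with no new data. Local-laboratory results, which Protocol 3.3 allows for assessing the reason for discontinuation, would remain outside the table because 13.3 is restricted to central results.
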